15.0 Incomplete Disclosure or Deception

15.1 Incomplete Disclosure or Deception:

- Not Applicable.

16.0 Potential Benefits to Participants

16.1 Potential Benefits:

The research participants may not see a direct benefit as a result of participation in the proposed study. However, research participants may benefit if they utilize the full-service mobile market, which may increase affordable food access, dietary intake, food security, and food purchasing outcomes. The mobile market will operate at the site locations recruited for this study after randomization/start-up for intervention sites and after final data collection for waitlist sites until the trial is complete. Then the sites will remain mobile market stops if they are well utilized and the community partners continue to wish to have mobile market service.

17.0 Statistical Considerations

17.1 Data Analysis Plan: See section 17.3

17.2 Power Analysis:

Power calculation. For the primary outcome of change in HEI scores, power is computed based on a t-test at the individual client level, but the sample size is inflated for the group randomization design by a factor of $1+(m-1)*ICC$ where m is the average cluster size and ICC is the intraclass correlation. In Co-Investigator [name]'s study with participants similar to the proposed study (i.e., from the same communities with similar income and diversity levels), the HEI SD was 11.2.⁹⁰ In our preliminary customer intercept survey study, we found an ICC of 0.0004. Therefore, to be conservative, we assume an SD of 12 and an ICC of 0.01. Under these assumptions with a two-sided type I error rate of 5%, this study will have 80% power to detect a mean difference of 5.5 HEI points between intervention and control participants with an average cluster size m of 20 and number of clusters k of 12 for a total of 264 participants (132 per group). This calculation assumes an attrition rate of 20%. Detection of a 5.0 point difference in HEI is clinically significant, as it corresponds to a lower risk of cardiovascular mortality and lower risk of all-cause mortality.¹²² Additionally, given our conservative approach, we may ultimately be adequately powered to detect even smaller differences in HEI scores between intervention and control sites.

17.3 Statistical Analysis:

Aim 1: The primary analysis will compare the mean within-person, baseline to follow-up change in HEI-2015 between the mobile market and waitlist control groups. Changes in HEI-2015 will be modeled via a Generalized Estimating Equation (GEE) linear model to account for the possible correlation of outcomes within community sites. Food insecurity, as measured by the U.S. Adult Food Security Survey Module, will be analyzed similarly. Baseline characteristics of randomized

SOCIAL PROTOCOL (HRP-580)

PROTOCOL TITLE: Mobile Food Market Cluster Randomized Trial

VERSION DATE: 1/5/2023

groups will be summarized to assess whether any chance imbalances between groups are scientifically meaningful. If necessary, imbalanced variables will be adjusted for in outcome analyses. For variables with > 10% missing values, we will compare characteristics between individuals with missing and non-missing values and perform multiple imputation if needed.¹²³ Since several hypotheses on different outcomes are of interest, we will focus mainly on reporting confidence intervals rather than null hypothesis significance testing, an approach in line with current recommendations.¹²⁴ If the overall intervention effect is sufficiently large (i.e., of similar clinically meaningful size that we are powered to detect), we will use exploratory analyses to assess the presence and magnitude of possible treatment-covariate interactions, where again the focus will remain on identifying interactions of a clinically meaningful magnitude rather than those that achieve a pre-determined significance threshold. In particular, we will investigate the influence of sex as a biological variable by assessing whether intervention effects vary by sex. While the primary analyses will be conducted within an intent-to-treat (as randomized) framework, we will also perform dose-adjusted analyses to investigate the association between frequency and volume of use of the mobile market and the outcomes of interest, and whether these usage measures mediate the effects of the intervention.¹²⁵ For process and implementation measures taken at the site level, the focus will be mainly on creating meaningful descriptive statistics and visualizations.

Aim 2: The main purchasing outcomes will be the average number of servings of fruits and vegetables purchased each week. These outcomes will be treated as continuous variables and modeled using mixed effects regression models with random effects for participant, site, and time. Initially, we will fit separate models for each outcome (average fruit, and vegetable servings purchased each week); we will also consider joint outcome models that use the vector of servings (fruit, vegetables) as the outcome. These models will be used to assess whether temporal trends in food purchases are different between study groups, and whether any differences in trends identified are modified by other baseline covariates, including sex as a biological variable. If any outcomes are zero-inflated, we will consider regression models which accommodate this, e.g., negative binomial regression. Similar approaches will be used to analyze intervention effects on other purchasing outcomes. Further, we will perform exploratory analyses to identify trends and patterns in intervention site participant mobile market purchases (tracked with customer loyalty cards) over the 6 month intervention period.

Aim 3: Quantitative statistical procedures and analysis. We will use mixed effects (i.e., repeated measures) models similar to those in Aim 2 to quantify associations between personal, social, environmental, and behavioral factors and the quantitative shopping adoption outcome measures for intervention group participants. We will construct both univariate and multivariate models to consider the independent and joint effects of each of these explanatory factors, along with exploring other potential predictors of shopping adoption (e.g., sociodemographic

SOCIAL PROTOCOL (HRP-580)

PROTOCOL TITLE: Mobile Food Market Cluster Randomized Trial

VERSION DATE: 1/5/2023

characteristics, dietary quality, food insecurity). We will also perform additional analyses to quantify joint associations between baseline factors, shopping adoption, and perceived mobile market features at follow-up.

Aim 3. Qualitative analysis procedures and analysis. Interviews will be transcribed verbatim and verified for accuracy.¹²⁶ Transcripts will be analyzed separately for high and low adopters using conventional content analysis¹²⁷ to identify major themes/subthemes. A team approach with two coders will facilitate analysis quality and rigor allowing for clearer and deeper understanding to be reached.¹²⁸ Prior to analysis, both coders will document personal preconceptions, topic knowledge, and feelings related to the study to facilitate objectivity.^{128,129} Then, a two-step process will be used. First, transcripts will be reviewed to identify themes. Second, coders will independently read each transcript several times and code responses into the themes identified in step one using qualitative data analysis software.¹²⁷ Codes assigned by the coders will be compared, and discrepancies in coding will be discussed to reach consensus.^{130,131} Next, the investigator team will compare themes and subthemes between high and low market adopters and assess for convergences and divergences between quantitative and qualitative findings. Similarities and differences will be detailed and supported with exemplar quotes. Additionally, as noted as part of the process evaluation, all intervention participants will answer open-ended qualitative questions about features that make the market helpful and suggestions for improvement. This opened-ended qualitative process data will provide further insights on mobile market implementation. This data will be analyzed apart from the qualitative interviews; however, content analysis and methods described above will be used to generate themes of findings from the data.¹²⁷

17.4 Data Integrity:

Data collection is the responsibility of the study staff under the supervision of the study investigator. The investigator is responsible for ensuring the accuracy, completeness, legibility, and timeliness of the data reported. Data collected in the field from participants will be collected primarily via web-based REDCap surveys completed on iPads with paper-pen back-ups in case of technical failure. If needed the paper-pen surveys will be entered into the secure REDcap Database by two different study staff and verified for accuracy.

Data will be extracted from the REDCap study database and prepared for analysis in the statistical software R.¹³² Data quality checks will be performed to identify potential data entry errors. A comprehensive data dictionary will be maintained as a standalone CSV, allowing variables to be read and properly labeled by any statistical software program.

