3.0 Study Endpoints/Events/Outcomes

3.1 Primary Endpoint/Event/Outcome:

Diet quality. Trained research staff certified in collecting dietary recalls using Nutrition Data System for Research software will collect three 24-hour dietary recall interviews (2 weekdays, 1 weekend day) from each participant at each measurement period (baseline and follow up). Dietary recall data will be used to calculate the Health Eating Index-2015 Score. HEI-2015 is a scoring system designed to measure adherence to the 2015-2020 Dietary Guidelines for Americans (2015-2020 DGA).^{69,70}

3.2 Secondary Endpoint(s)/Event(s)/Outcome(s):

Food insecurity. Food insecurity in the past 6 months will be measured with the gold-standard, 18-item food security screening module of the USDA, which will allow for assessment of both binary food insecurity (yes, food insecure; no, food secure) and level of food security (very low, low, marginal, and high food security).⁹¹ We will also use newly developed and validated nutrition insecurity measures to assess **nutrition insecurity** in the past 6 months, which helps us understand fuller contexts around choices people may make when money is tight (e.g., compromise nutrition for a full stomach).¹³⁷

Fruit & Vegetable purchasing outcomes: Participants will record their fruit and vegetable purchases using forms in a provided booklet, and mail their booklets to the researchers in prepaid addressed envelopes, which will be used to measure:

- Average weekly servings of fruits and vegetables purchased
- Total number of trips
- Store types visited

Mobile Market shopping patterns: Participants randomized to the intervention sites will participate in a “Market Members” program, which tracks their purchases at the Mobile Market (i.e. number of transactions, items purchased, dollars spent).

Personal, social, behavioral, and environmental factors that may influence mobile market adoption. These factors include:

- Neighborhood Healthy Food Availability (4 item scale; $\alpha=0.89$);⁹⁹
- Social Connectedness (8 item scale, $\alpha=0.92$);¹⁰²
- Health-related quality of life (4-items);¹⁰³⁻¹⁰⁷
- Self-efficacy of Healthy Cooking (4 item scale, $\alpha=0.85$).¹⁰⁹
- Self-efficacy for eating and cooking fruits and vegetables (4 item scale, $\alpha=0.90$).¹⁰⁸
- Everyday Discrimination Scale (6 item scale $\alpha=0.77$ + 2 follow-up items)¹³⁹⁻¹⁴⁰

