11.0 Number of Participants

11.1 Number of Participants to be Consented:

Targeting enrollment at 264 participants in full-data collection.

For qualitative interviews, these will happen with a smaller subsample of participants enrolled. Specifically, the qualitative sample will be derived from purposive sampling of extremes^{119,120} in market adoption. Thus, participants selected for interviews will be from the highest and lowest quintiles of market shopping as measured by the number of trips to the Mobile Market during the final two months of the intervention period. The estimated number of interviews is 24 for low adopters and 24 for high adopters (48 total) selected from across intervention sites,¹²¹ however, the qualitative sample size will only be set after saturation has occurred during analysis and coding of the qualitative data.¹²¹

For our primary outcome, with our planned sample size of 264 divided between 12 clusters, we anticipate 80% power to detect a difference of 5.0 HEI points between the intervention and control groups. This calculation assumes an attrition rate of 15%, so that our final analytic sample size is 224 individuals, and a conservative ICC of 0.01. If attrition is higher or recruitment is slower, a final analytic sample of n=160 individuals will provide 80% power to detect a difference of 6.0 HEI points, which is still within the range of plausibility for the effect size of this intervention.

Furthermore, smaller effects will be detectable even with this smaller sample if the ICC is closer to the value 0.004 observed in previous studies. Additionally, for our secondary outcomes, an even smaller sample would be acceptable for analysis. For example, for the third aim, we are aiming for 24 high mobile market shopping adopters and 24 low mobile market shopping adopters (final sample size will be determined once saturation is reached).

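### The primary analysis compares raw HEI-2015 change with no prespecified baseline HEI-2015 covariate, which gives up precision available at almost no cost

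*Combined protocol and SAP*

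**What the plan says.** Section 17.3 (Aim 1) defines the primary contrast: "The primary analysis will compare the mean within-person, baseline to follow-up change in HEI-2015 between the mobile market and waitlist control groups". On the model it says: "Changes in HEI-2015 will be modeled via a Generalized Estimating Equation (GEE) linear model", with clustering on community site. No covariate is named.

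Adjustment is conditional. Baseline characteristics of the randomised "groups will be summarized to assess whether any chance imbalances between groups are scientifically meaningful", and then: "If necessary, imbalanced variables will be adjusted for in outcome analyses". There is no list of variables and no numerical trigger.

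Baseline HEI-2015 will be available. Section 3.1 plans "three 24-hour dietary recall interviews (2 weekdays, 1 weekend day) from each participant at each measurement period (baseline and follow up"). Nothing elsewhere puts it in the primary model. Dietary quality appears as a predictor only in Aim 3, for shopping adoption.

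On size, section 11.1 claims 80% power for 5.0 points with 224 analysed, and adds a fallback: "a final analytic sample of n=160 individuals will provide 80% power to detect a difference of 6.0 HEI points". Section 17.2 describes a 5.0-point difference as clinically significant.

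**The concern.** Subtracting baseline forces its regression slope to be 1. With equal SDs at the two visits, the efficient slope is the correlation ρ, which is below 1 for any diet score measured with error. The change score therefore carries avoidable noise.

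That gain exists whether or not the arms look balanced, so observed imbalance is the wrong criterion for including baseline HEI. The rule also leaves the covariates of the primary model to a judgement made after baseline data have been seen.

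Section 17.3 says reporting will rest mainly on confidence intervals, so the cost falls on the main result. It matters most in the fallback of 160 analysed, where the plan accepts a detectable difference above the 5.0 points it treats as clinically significant.

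**Working it through.** **Inputs from the documents.** SD 12, ICC 0.01, 12 sites, two-sided 5%, 80% power, individual-level test with design effect 1+(m−1)·ICC (17.2). Analysed samples of 224 and 160 (11.1).

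**Assumed.** ρ = 0.3, 0.5, 0.7; equal SDs at both visits; the same ICC for both estimators.

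**The plan's own figures first.** Detectable difference = (1.960+0.842)·SD·√(4·DE/n), with DE = 1+(n/12−1)·0.01.

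- n=224: DE = 1.177, giving 2.802·12·√(4·1.177/224) = 4.87 points. Power at 5.0 is 82%, so the 11.1 claim reproduces.
- n=160: DE = 1.123, giving 5.63 points. Power at 6.0 is about 85%, a little better than claimed.

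(17.2 separately claims "80% power to detect a mean difference of 5.5 HEI points between intervention and control participants". With 20% attrition from 264, about 211 are analysed and the stated method gives 85–87%. That mismatch does not bear on this point.)

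**Gain from the covariate.** With s the SD of a single HEI score:

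- Var(change) ∝ 2s²(1−ρ)
- Var(adjusted) ∝ s²(1−ρ²)
- Ratio = (1+ρ)/2 = 0.65, 0.75, 0.85
- Interval width ratio = √ratio = 0.81, 0.87, 0.92

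**If SD 12 is the SD of a single score.** Section 17.2 takes it from an HEI SD of 11.2 that is not described as an SD of change. Each cell is change score → adjusted.

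| ρ | SD | Detectable, n=224 | Detectable, n=160 | Power at 5.0, n=160 (normal) | Same, t with 10 df |
|---|---|---|---|---|---|
| 0.3 | 14.20 → 11.45 | 5.77 → 4.65 | 6.67 → 5.37 | 56% → 74% | 48% → 65% |
| 0.5 | 12.00 → 10.39 | 4.87 → 4.22 | 5.63 → 4.88 | 70% → 82% | 61% → 74% |
| 0.7 | 9.30 → 8.57 | 3.77 → 3.48 | 4.36 → 4.02 | 89% → 94% | 82% → 88% |

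**If SD 12 is the SD of change.** For ρ = 0.3, 0.5, 0.7:

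- n=224: 4.87 unadjusted against 3.93, 4.22, 4.49 adjusted.
- n=160: 5.63 unadjusted against 4.54, 4.88, 5.19 adjusted.

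**Simulation, n=224.** 12 sites, SD 12, ICC 0.01, 2,000 runs per cell, independence working correlation, Kauermann-Carroll standard errors, t with 10 df. Empirical SE, change against adjusted: 2.05 v 1.67, 1.75 v 1.50, 1.33 v 1.24. Null rejection was 4.1–4.7% for change and 4.5–5.0% for adjusted.

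**Second simulation.** 12 clusters of 18, exchangeable GEE with bias-reduced standard errors, 1,000 runs per ρ. Power at 5.0 points was 51% v 68%, 66% v 78% and 87% v 91%, with type I error of about 3–4% for both.

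**Degrees of freedom.** Even charging a whole site-level df (critical t from 2.228 to 2.262) widens the interval by 1.5%. Break-even needs (1+ρ)/2 = 1/1.0153², so ρ of about 0.94.

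**The case against.** The planned analysis is valid, and at 224 analysed it already meets 5.0 points by the plan's own method. This is a choice between two accepted estimators of the same effect. That stands, and it is why the point is about efficiency and prespecification only.

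Three objections bear on the size of the gain:

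- **Power method.** The normal-approximation powers are optimistic for 12 sites. With 10 df, the n=160 figure at ρ = 0.5 rises from 61% to 74% and does not reach 80%. The relative gain survives, but adjustment does not by itself restore the fallback to 80% power for 5.0 points at that ρ.
- **SD reading.** Section 17.2 introduces its calculation as one for change in HEI, so SD 12 may be an SD of change. On that reading adjustment at n=160 and ρ = 0.7 still gives 5.19, above 5.0.
- **Site effects.** Subtraction removes stable site differences fully, while a covariate with slope ρ removes only part. With perfectly stable site effects the variance ratio becomes (1+ρ)/2 + (m−1)·ICC·(1−ρ)/2. At n=224 (m = 18.67) and ICC 0.01 this gives 0.71, 0.79 and 0.88. At an assumed ICC of 0.05 it is 0.96–0.98, and the gain vanishes when (m−1)·ICC = 1, an ICC of about 0.057. The plan's own ICC is well below that.

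It may also be said that imputation, which 17.3 allows for variables with more than 10% missing, complicates the claim that nobody is lost. But a missing baseline HEI also leaves the change score missing, so both models face the same imputation.

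**Conclusion.** The concern holds. The primary model omits an available baseline covariate and ties adjustment to an undefined imbalance judgement. Prespecifying baseline HEI-2015 would narrow the primary interval by 19%, 13% or 8% at ρ = 0.3, 0.5 or 0.7. If site effects are perfectly stable at ICC 0.01, the narrowing is about 16%, 11% or 6% (√0.71, √0.79, √0.88).

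The direction is secure at the plan's ICC, for either reading of SD 12 and for any ρ below about 0.94 even if a full site-level df is charged. The size is not, because the documents give neither ρ nor the stability of site effects over time. The change should be made, but the planned analysis is not invalid without it.

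**What to change.** In section 17.3:

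1. Make the primary model follow-up HEI-2015 (equivalently, change) on arm with baseline HEI-2015 as a prespecified covariate, clustered on site, whatever the observed balance. Use a small-sample correction suited to 12 sites.
2. Replace the conditional adjustment sentence with a short fixed covariate list for the primary model. Baseline HEI-2015 alone is enough.
3. Report the unadjusted change comparison as a sensitivity analysis.
4. Treat wave and site type as optional, for example in a further sensitivity analysis with small-sample df. Site type is the stratification factor in 9.1, but the two together use 3–4 of the 10 site-level df, and the documents give no variance by wave or site type to show a gain.

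The cost is SAP wording. No new data are needed, and no participant with a change score is lost. Baseline HEI varies between individuals and uses essentially no site-level df. The list must stay short, because 12 sites would not support a long one.

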5.0 Procedures Involved

5.1 Study Design:

We will use a cluster randomized trial design. We will recruit 12 community sites (“clusters”) in low-income neighborhoods and/or adjacent to low-income housing residences with 22 participants per site. To enhance feasibility, we will conduct the study in three waves, with 4 community sites in wave 1, 4 community sites in wave

2, and 4 community sites in wave 3. For each wave, following participant baseline data collection that will occur at the same time across the sites of the wave, we will randomize sites to receive the full-service market intervention or serve as a waitlist control. Sites randomized to receive the market will begin weekly service immediately following 2 months of strategic community engagement led by the community partner at The Food Group with the Mobile Market (see section 4 above). After 6 months of market operation, follow-up data collection will occur for outcome measurement followed by qualitative interviews with a subset of intervention participants (high and low adopters). The RE-AIM (reach, effectiveness, adoption, implementation, maintenance) framework guides our evaluation.⁸⁷⁻⁸⁹ This process will be repeated for Wave 2 and 3 sites. Intervention sites will continue to receive the market during and after the follow-up data collection period. The waitlist sites for Waves 1, 2, and 3 will receive the intervention following final data collection for the wave.

5.2 Study Procedures:

Recruitment of sites: See details in IRB protocol section 9.0 and 12.

Recruitment of individuals from sites recruited for the trial. See details in IRB protocol section 9.0 and 12. See also “eligibility screening script” document.

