9.0 Study Population

9.1 Inclusion Criteria:

To achieve the proposed study aims, communities and human subjects from those communities will be recruited and data about operational procedures and costs will be collected.

Community site selection (see letters of support of interested site locations):

In order to be eligible to participate in this study, a community site (e.g., public housing hi-rise, low-income senior living residence) must meet the following criteria:

- (a) locale for low-income populations that experience difficulty in accessing healthy, affordable foods (e.g., public housing residences; low-income senior housing) or a community center in a low-income, low-food access (0.5 mile) census tract;
- (b) willingness to be randomized to the intervention or waitlist control;
- (c) located over 0.5 miles apart from other trial sites;
- (d) willingness to allow for recruitment and data collection to occur in onsite community rooms;

Process for initial contact with sites:

[name] at The Food Group with the Twin Cities Mobile Market regularly receives calls from site locations across the Twin Cities that may be interested in having the mobile market come. As these calls come in, she will provide information on the mobile market service in general and also that there is a research study opportunity. She'll provide the sites a site flyer. She will connect any interested sites with the Mobile Market researchers for specific questions related to the research, if any, prior to the formal conversation, as outlined in the attached site screening script (below).

Flyer for site recruitment: We have created a flyer for sites (attached) interested in mobile market service study to provide information on the mobile market research study. This site flyer would serve as a preview to a more formal conversation about being both a mobile market site and research site. It should be noted that the site recruitment flyer lists the contact information for Co-Investigator [name] given her position of regularly receiving this type of call at the Mobile Market currently. She will refer sites to the researchers for research specific questions as they arise prior to a formal conversation as outlined with the screening script.

Site screening script:

SOCIAL PROTOCOL (HRP-580)

PROTOCOL TITLE: Mobile Food Market Cluster Randomized Trial

VERSION DATE: 1/5/2023

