For sites that may be interested, a research team member and Co-Investigator [name] will go through a formal conversation using the site screening script to guide the conversation. Please see the site screening script attached.

When sites would like to join:

If an interested site were to be interested, eligible and decide to participate, a letter of support would be written documenting this decision. This letter of support will be provided to the UMN IRB following signature.

Sites meeting site eligibility criteria will be recruited in three waves, with 4 sites in wave 1, 4 sites in wave 2, and 4 sites in wave 3. After baseline data collection for each Wave, stratified randomization of sites by type (e.g., randomization within public housing, low-income senior living sites) will be conducted to ensure balance between groups. See support letters from sites on the market waitlist meeting the aforementioned criteria.

Human subject recruitment will occur in the participating communities.

In order to be eligible to participate in this study, an individual must meet the following criteria:

- (a) being aged 18 years or older;
- (b) identifying as the primary food shopper in their household;
- (c) being able to speak English or American Sign Language (ASL);
- (d) living within a half mile of the community site location; and
- (e) reporting to be likely or somewhat likely to shop at the market in response to:
“how likely would you be to shop regularly at the Twin Cities Mobile Market if it came to your neighborhood each week (response options: likely to unlikely).
- (f) willing and able to participate in all study data collection activities
 - Please note: we may be amending these inclusion criteria and this protocol and all documents to include individuals who speak other languages once the community sites are selected and the other languages are known.

9.2 Exclusion Criteria: An individual who meets any of the following criteria will be excluded from participation in this study:

- (a) planning to move in the next 12 months
- (b) not currently shopping at the mobile market
- (c) not having a phone number or mailing address
- (d) presence of a condition or abnormality that would prohibit participation in the study or the quality of the data

9.3 Screening: Screening will occur in person or via phone using the eligibility screening script (attached). Participants will self-report answers to these questions.

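### The primary GEE on 12 sites names no variance estimator, small-sample correction or reference distribution; the usual GEE interval would carry about 10-11% two-sided error instead of 5%.

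*Combined protocol and SAP*

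**What the plan says.** - **Model.** Section 17.3, Aim 1, compares mean within-person change between groups: "Changes in HEI-2015 will be modeled via a Generalized Estimating Equation (GEE) linear model", to allow for correlation within sites. Food insecurity is to be analysed in the same way. Sections 17.3 and 17.4 give no working correlation, variance estimator, small-sample correction, reference distribution or degrees of freedom. The only software named is R.
- **Clusters.** Section 5.1: "We will recruit 12 community sites", with 22 participants each. Section 17.2 gives 132 participants per group, which implies 132/22 = 6 sites per arm.
- **Randomisation.** Section 5.1: "we will conduct the study in three waves", with four sites in each. Section 9.1 adds "stratified randomization of sites by type (e.g., randomization within public housing, low-income senior living sites) will be conducted to ensure balance between groups". Neither factor is named in the primary model. The covariate rule in 17.3 covers only baseline variables found to be imbalanced.
- **Error rate and reporting.** Section 17.2 sets a two-sided type I error of 5%. No interval level is printed, so 95% is inferred from that. Section 17.3 puts the emphasis on intervals over significance tests.
- **Target effects.** Section 11.1: "we anticipate 80% power to detect a difference of 5.0 HEI points between the intervention and control groups", with 224 analysed. Section 17.2 states 80% power for 5.5 points with 20% attrition, and adds: "Detection of a 5.0 point difference in HEI is clinically significant".

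**The concern.** The sandwich variance is justified when there are many clusters. With 12 it is biased downwards and is itself noisy, and a normal quantile ignores both problems. Software commonly reports this uncorrected form, so an analyst who follows 17.3 as written could use it in good faith. The ICC offers no protection, because the difficulty is the number of sites and not the strength of clustering. Since the interval carries the primary result, its coverage is what is at stake. The choice of standard error would also still be open when the data are seen.

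**Working it through.** **Inputs.** From 17.2: SD 12, ICC 0.01, two-sided 5%, 12 clusters. From 11.1: 224 analysed, so 224/12 = 18.67 per site. Assumed: normal outcomes, SD 12 for the change score, six sites per arm.

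**The plan's own power first.** Section 17.2 inflates by 1 + (m − 1) × ICC.
- At 224 analysed: 1 + 17.67 × 0.01 = 1.177. SE = 12 × √(4 × 1.177/224) = 1.739. Then 5.0/1.739 = 2.875, and normal-theory power is Φ(2.875 − 1.96) = 82%. The 80% in 11.1 reproduces.
- At 264 × 0.80 = 211 analysed: inflation 1.166 and SE 1.784. Then 5.5/1.784 = 3.083, and power is 87%. The 80% in 17.2 is lower than its own formula gives.

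**Error of the uncorrected interval, treatment-only model.** With equal clusters the estimate is a difference of two means of six site means. The uncorrected sandwich divides each arm's sum of squares by 6 where 5 would be unbiased, so its variance is 10/12 of the unbiased one. The true reference is t on 10 df. Hence:

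error = 2 × P(t10 > 1.96 × √(10/12)) = 2 × P(t10 > 1.789) = 10.4%.

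Simulation with unequal site sizes and an estimated exchangeable correlation gives 10.4-10.7% at ICC 0.0004, 0.01 and 0.05. A separate simulation gives coverage of 89.0-90.0% over the same ICCs, and a standard GEE routine gives 88.9% in 1,000 runs.

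**Effect of each part of the correction (coverage, treatment-only).**

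| Variance | Reference | Coverage |
|---|---|---|
| Uncorrected | normal | 89.0-90.0% |
| Uncorrected | t10 | 92.6-93.4% |
| Kauermann-Carroll | normal | 91.8-92.4% |
| Mancl-DeRouen | normal | 94.0-94.6% |
| Kauermann-Carroll | t10 | 94.6-95.3% |

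**Strata left out of the model.** Section 17.2 uses 0.01 as the total ICC, so any wave or site-type variance is part of it. Holding the total at 0.01 and placing half or all of it between strata gives about 8-9.5% error uncorrected, and about 4% with Kauermann-Carroll and t10. Omitting the terms therefore moves the interval in the conservative direction.

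**Strata added without a correction.** With wave terms the error is 2 × P(t8 > 1.96 × √(8/12)) = 14.8%. With additive wave and two types it is 2 × P(t7 > 1.96 × √(7/12)) = 17.8%. The plan does not call for this; it shows why stratum terms should not go in alone.

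**Interval width.** The mean of an estimated SE on 10 df is 0.975 of its target.
- Uncorrected: 1.96 × 1.739 × √(10/12) × 0.975 = 3.0 points.
- Kauermann-Carroll with t10: 2.228 × 1.739 × 0.975 = 3.8 points.

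**Where it changes the reading.** Share of simulated trials (true difference 5 points) whose interval excludes zero, by size of estimate:

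| Estimate (HEI points) | Uncorrected | Kauermann-Carroll, t10 |
|---|---|---|
| 3.0-3.5 | 63% | 27% |
| 3.5-4.0 | 84% | 51% |
| 4.5-5.5 | 99% | 91% |

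**Power with t10 (noncentral t).** For 5.0 points at 224: 74%. For 5.5 points at 211: 79%.

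**The case against.** The strongest reply is that 17.3 does not forbid a correction, and that a statistician experienced with cluster trials would apply one. That is fair, and it is why no error rate can be charged to the plan as such: 10-11% belongs to the usual interval if it is used. But nothing commits to the alternative.

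A second reply is that the result matters little near the target effect. This also stands in part. Estimates of 4.5-5.5 points usually exclude zero either way, and with no market effect an estimate of 5 or more in either direction arises in only about 0.4% of trials. The exposure is at smaller estimates, which 17.2 says the trial may be able to detect.

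A reader might infer more than the documents support:
- **That leaving wave and site type out of the model causes undercoverage.** It does not; it makes the interval conservative. Adding them is a choice about precision.
- **That the error could be anywhere from about 1% to over 20%.** The low end comes from adding wave or type effects on top of an ICC of 0.01, which implies a total ICC of about 0.04-0.07, several times the value that 17.2 calls conservative. The high end comes from stratum terms without a correction, which the plan does not propose.
- **That the stratified degrees of freedom are settled.** Seven df assumes additive wave and two-type effects. Section 9.1 gives its types only as examples, and its site criteria also admit "or a community center in a low-income, low-food access (0.5 mile) census tract".

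**Conclusion.** The concern holds, and 17.3 should be amended before unblinding. With 12 sites, the usual GEE interval has about 10-11% two-sided error (about 8-9.5% if part of the 0.01 ICC lies between strata), against the 5% of 17.2. Its half-width is about 0.8 points too small (3.8 − 3.0). Kauermann-Carroll with t10 restores coverage to about 95%. The coverage result barely depends on the ICC; the widths and power rest on SD 12, ICC 0.01 and the retained numbers in the plan. The consequence is real for estimates of about 3-4 points and small near 5, so this is a correction to make, not a reason to doubt the design.

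**What to change.** State in 17.3 that the primary GEE uses a bias-corrected sandwich standard error (for example Kauermann-Carroll; another validated correction would serve) and a t reference on 12 minus the number of cluster-level parameters, which is 10 df for treatment only. Print the interval level. Use the same standard error and reference for the food-insecurity GEE.

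Wave and the site-type strata actually used in randomisation may be added to recover precision if strata differ. In that case, name them in advance, keep the correction, and reduce the df to match: 7 for additive wave plus two types.

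The cost is a few sentences, a wider interval (half-width about 3.8 points instead of 3.0) and restated power. With t10, power is about 74% for 5.0 points at 224 analysed (11.1 says 80%) and about 79% for 5.5 points at 211 (17.2 says 80%). So the 17.2 claim nearly survives and the 11.1 claim does not. Stratum terms lower power further when strata do not differ: about 69% for 5.0 points with 7 df. No new data, sites or participants are needed.
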